11. SAFETY

The secondary safety endpoints are the following:

- Incidence of CSF leaks within 60 (+3) days post-operatively
 - Incidence of AEs up to 60 (+3) days post-operatively
 - Incidence of SSIs according to US NHSN within 30 (+3) days post-operatively
-
- 

- Number of unplanned interventions within 30 (+3) days post-operatively
- Laboratory values and vital signs (e.g., elevated WBC count, fever [temperature >100.7°F or 38.2°C], tachycardia [pulse >100], hypotension [mean arterial pressure <60]).

The logistic regression approach used for the primary efficacy endpoint will be used to calculate the proportions of patients with: incidence of CSF leaks within 60 (+3) days post-operatively, and incidence of SSIs according to NHSN within 30 (+3) days postoperatively. The number of unplanned interventions within 30 (+3) days post-operatively will be compared between the 2 treatment groups using a Wilcoxon rank sum test.

The duration and incidence of each laboratory and vital sign abnormality will be recorded. Abnormal laboratory values will be observed, followed, and managed by the investigator for a return to baseline, per standard of care. Clinical laboratory parameters and vital signs will be summarized by visit and treatment group. Absolute values and changes from baseline will be presented. Shift tables for baseline vs. worst post baseline assessment (normal, abnormal/not clinically significant, abnormal/clinically significant) will be generated for laboratory parameters.

An AE overview summary table will be prepared including the number of patients reporting an AE, the percentage of patients (%) with an AE, and the number of events reported, for the following categories:

1. Deaths.
2. SAEs.
3. AEs leading to withdrawal.
4. Severe AEs.
5. Related AEs.
6. AEs of special interest.

Adverse events will be tabulated by body system using the Medical Dictionary for Regulatory Activities (MedDRA). The table will display the total number of patients reporting an AE, the percentage of patients (%) with an AE, and the number of events reported by system organ class (SOC) and preferred term. In addition, tables will be

summarized by SOC, preferred term, severity grade (mild, moderate, and severe) and relatedness to treatment (“possibly related” or “probably related” AEs, and AEs with missing information on relatedness will be considered “related”; “unlikely related” or “not related” AEs will be considered “not related”). These tables will be produced for:

- All AEs
- AEs with an incidence $\geq 5\%$ of patients in any treatment arm
- Non-serious AEs with an incidence $\geq 5\%$ of patients in any treatment arm
- AEs by causality (related/unrelated)
- AEs leading to death
- AEs by severity
- SAEs
- AEs leading to withdrawal

Listings will be prepared for:

- All AEs sorted by center and patient
- SAEs
- AEs leading to death
- AEs leading to withdrawal
- Laboratory results and vital signs

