2.2 Secondary Objective

The secondary objective of this study is to evaluate the safety of FS VH S/D 500 s-apr compared to DuraSeal Dural Sealant as an adjunct to sutured dural closure.

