5.3 Sample Size

The number of subjects in a clinical trial should always be large enough to provide a reliable answer to the questions addressed. This number is usually determined by the primary objective of the trial. If the sample size is determined on some other basis, then this should be made clear and justified. For example, a trial sized on the basis of safety questions or requirements or important secondary objectives may need larger numbers of subjects than a trial sized on the basis of the primary efficacy question (see ICH E1A).

This study is designed to show non-inferiority (NI) of FS VH S/D 500 s-apr compared to DuraSeal Dural Sealant based on the primary composite efficacy endpoint. The

proportion of patients meeting the composite primary endpoint is assumed to be █% for FS VH S/D 500 s-apr and █% for DuraSeal. Using a non-inferiority margin of 10% (the largest clinically acceptable difference), a 1-sided Type 1 error rate (α) of 2.5%, a statistical power ($1-\beta$) of 80%, that one interim analysis is performed after 50% of the patients complete the study, the sample size estimation results in 202 evaluable patients. Assuming a group sequential design utilizing O'Brien-Fleming boundaries, the study may be stopped early for futility if a p-value >0.2486 is observed at the interim. The estimation of sample size was performed using SAS 9.4 software (SAS Institute; Cary, NC). The primary analysis will be performed on the per protocol analysis set (PPS). Assuming that the PPS is 10% less than the total number of randomized subjects, 112 patients per treatment group should be randomized, and there will be 224 patients in total.

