5.4 Randomization Procedure

Patients will be randomly assigned to FS VH S/D 500 s-apr or DuraSeal Dural Sealant at a ratio of 1:1. Randomization will be stratified by study center and surgical region (PF or ST) with the goal of achieving an approximate 3:1 ratio (ST:PF) of the 2 surgical regions in the randomized study population. Randomization will be controlled via an interactive Webresponse system (IWRS), [REDACTED] using dynamic allocation. On the day of surgery (Day 0), upon confirmation of pre-operative eligibility criteria, a member of the site study staff other than the surgeon will obtain a treatment assignment from the IWRS. Adequate amounts of FS VH S/D 500 s-apr and DuraSeal Dural Sealant will be taken into the operating room for potential use as the study treatment.

Immediately after the patient's intra-operative eligibility for study treatment has been confirmed (ie, spontaneous CSF leak or CSF leak after Valsalva maneuver), the assigned treatment will be revealed to the surgeon and the assigned IP or control will be applied to the CSF leak site. Following surgery, the treatment assignment and the actual treatment applied will be entered in the eCRF for the patient. If the patient's eligibility is not confirmed intra-operatively, the operation will be performed according to hospital standards. The study site designee will document the noncompliant criterion or criteria plus the date and reason(s) for the patient's exclusion in the eCRF, and an entry will be made in the IWRS that the study treatment was not administered.

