5.6 Safety Assessments

The following secondary safety assessments will be performed during this study:

- Incidence of CSF leaks within 60 (+3) days post-operatively
- Incidence of AEs up to 60 (+3) days post-operatively
- Incidence of SSI according to US NHSN within 30 (+3) days post-operatively
- Number of unplanned interventions within 30 (+3) days post-operatively
- Laboratory values and vital signs (e.g., elevated WBC count, fever [temperature >100.7°F or 38.2°C], tachycardia [pulse >100], hypotension [mean arterial pressure <60]).

Unplanned interventions include meningitis, the management of a deep infection, minimally invasive procedures, and the return to the operating room for neurosurgical complications other than a CSF leak or pseudomeningocele formation, or those related to the subject's pre-existing condition during the 30-day follow-up period following original surgical procedure.

Surgical site infections will be evaluated by the surgeon or designated physician according to CDC/NHSN criteria.

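### Unplanned interventions are compared between arms only by a Wilcoxon rank sum test, with no between-group estimate or confidence interval, and that test responds little to repeat interventions

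*SAP*

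**What the plan says.** Protocol 2.2 makes safety a comparative question: "The secondary objective of this study is to evaluate the safety of FS VH S/D 500 s-apr compared to DuraSeal Dural Sealant". One of the five secondary safety endpoints in SAP section 11 is a count: "Number of unplanned interventions within 30 (+3) days post-operatively". SAP 5.6 describes what is counted: "Unplanned interventions include meningitis, the management of a deep infection, minimally invasive procedures", together with returns to the operating room for certain neurosurgical complications.

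The only between-group comparison specified for it, in the same words in Protocol 9.4.4 and SAP section 11, is: "The number of unplanned interventions within 30 (+3) days post-operatively will be compared between the 2 treatment groups using a Wilcoxon rank sum test". No significance level, sidedness, effect measure, interval, margin or power is given for this comparison.

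Other parts of the SAP bear on the point:

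- Section 7.1 summarises safety data by actual treatment: n, mean, SD, median, minimum and maximum for continuous variables, and frequencies and percentages for categorical ones.
- Section 13.1 plans Table 14.3 (secondary safety assessments) on the safety set.
- Section 13.2 plans listings of surgical revisions (16.2.6.5) and other interventions (16.2.6.7).
- Section 11 sends two neighbouring endpoints, 60-day CSF leaks and surgical site infections, to the logistic regression approach of the primary endpoint. In section 10.1 that approach yields a difference in proportions with a 95% confidence interval.

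**The concern.** A rank test gives a p-value but does not say how large a difference is or how large it could be. For a safety comparison those are the quantities a reader needs.

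The test also fits the named endpoint poorly. The endpoint is a number of interventions. If most patients have none, almost all values are tied at zero and the ranks mainly separate patients with no intervention from patients with any. Whether an affected patient had one intervention or three then moves the statistic very little. An excess on one arm that consists of repeat interventions in the same patients could leave the planned comparison almost unchanged.

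**Working it through.** **Inputs from the documents.** SAP 5.3 arrives at 202 evaluable patients, allows for a 10% loss between randomisation and the per-protocol set, and so fixes the number to randomise: "112 patients per treatment group should be randomized, and there will be 224 patients in total". SAP 5.4 gives 1:1 allocation. The safety set is all treated patients (SAP 6.2), so up to about 112 per arm.

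**Assumptions.** Two-sided 5% for the Wilcoxon test, the intervention rates, and a doubling as the effect of interest. None of these is in the documents, so ranges are shown.

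**The plan's own figure.** 202 / 0.9 = 224.4, against 224 stated (224 × 0.9 = 201.6). This agrees to rounding. No sample size or power is stated for unplanned interventions.

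**Step 1: the share affected doubles, at most one event per patient.** The count is then binary and a two-proportion formula applies: power = Φ[(d − 1.96·SE0)/SE1], with SE0 = √(2p̄(1−p̄)/n), SE1 = √([p1(1−p1) + p2(1−p2)]/n) and n = 112.

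- 5% v 10%: (0.05 − 1.96 × 0.0352)/0.0350 = −0.54, power 0.294, non-significant 71%.
- 10% v 20%: (0.10 − 1.96 × 0.0477)/0.0472 = 0.14, power 0.555, non-significant 45%.
- 20% v 40%: (0.20 − 1.96 × 0.0612)/0.0598 = 1.34, power 0.910, non-significant 9%.

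**Step 2: the Wilcoxon test itself, by simulation.** Tie-corrected, 112 per arm, 10,000 trials per case, test mean twice the control mean. Percentage non-significant:

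| Control mean | At most one event | Poisson counts | Overdispersed (negative binomial, shape 0.5) |
|---|---|---|---|
| 0.02 | 87 | 88 | 89 |
| 0.05 | 70 | 73 | 77 |
| 0.10 | 45 | 53 | 64 |
| 0.20 | 9 | 25 | 51 |

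The binary column agrees with step 1. For rare events, therefore, the low power comes mainly from the number of patients. By the same formula, 80% power for a doubling needs 435 per arm at 5% v 10% and 199 per arm at 10% v 20%.

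**Step 3: the same share affected, total doubled.** Control count = Bernoulli(0.10). Test count = Bernoulli(0.10) × (1 + Poisson(1)), so the means are 0.10 and 0.20. Wilcoxon power is about 5%, which is the nominal error rate. A test of the ratio of means with a robust standard error has power of about 36% on the same data. Here the choice of method matters.

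**Step 4: what a p-value alone leaves open.** With 11/112 affected on control and 21/112 on test, p = 0.057. The difference is 8.9 points with SE 0.0464, so the 95% upper limit is 8.9 + 1.96 × 4.64 = 18.0 points.

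**Step 5: what an interval would show.** If both arms had the same observed rate, the upper limit of the difference is 1.96 × √(2p(1−p)/112). This is 5.7 points at 5% and 7.9 points at 10%. With Poisson counts the upper limit of the rate ratio is exp(1.96 × √(2/(112p))), which is 3.2 and 2.3. A doubling is not excluded in either case.

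**The case against.** Three stronger readings are tempting, and the documents do not support them.

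- **That repeat interventions would be invisible.** By-arm summaries, Table 14.3 and the intervention listings are planned. If the count is summarised as continuous, the mean gives each arm's total, the maximum shows repeats, and n, mean and SD let a reader build an interval for the difference in means. Many of the underlying events would also appear in the adverse event tables. What is missing is a planned between-group estimate and interval.
- **That this trial's test misses a doubling in 45% to 71% of cases.** That range needs a control rate of 5% to 10%, and no rate is given. Minimally invasive procedures count, so a higher rate cannot be ruled out. The figure also follows from a plain two-proportion formula, so a test on proportions would do no better.
- **That a non-significant result will be taken as comparable safety.** Neither document says so.

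Two further points are fair. The contrast with CSF leaks and infections is partly inferred, because SAP section 11 says only that the logistic approach will be used to calculate proportions. The case in step 3 is constructed, and the documents do not suggest that such a pattern is expected.

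These points limit the size of the concern. They leave in place that a count endpoint under a comparative safety objective has a p-value as its only planned between-group result.

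**Conclusion.** The point holds as a gap in estimation and a mismatch between test and endpoint. It is an inexpensive improvement to one secondary safety endpoint and does not touch the primary analysis.

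The mismatch rests on most counts being zero. Under that condition and an assumed 10% affected in each arm, a doubled total is detected about 5% of the time by the planned test and about 36% by a robust rate ratio. For an ordinary doubling, the chance of a non-significant result runs from about 9% (control rate 20%, at most one event per patient) to about 89% (control mean 0.02). That spread is conditional on assumed rates and is driven mainly by the sample size. It is a reason to show an interval; it does not show that the Wilcoxon test is at fault.

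**What to change.** In Protocol 9.4.4 and SAP section 11, specify two estimates for unplanned interventions within 30 (+3) days, both reported in Table 14.3 on the safety set:

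- (a) the difference (Tisseel − DuraSeal) in the proportion of patients with at least one unplanned intervention, with a two-sided 95% confidence interval, using the primary logistic approach where it can be fitted;
- (b) the ratio of mean interventions per patient with a 95% confidence interval, from a Poisson model with robust standard errors or a negative binomial model.

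Only (b) responds to repeat interventions, so both are needed. Keep the Wilcoxon p-value as descriptive. No safety margin is implied, and none should be read into the limits.

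The cost is SAP and protocol wording and two rows in one table, from data already collected at the follow-up visits. The downside is that the intervals will be wide and will often not exclude a doubling.

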5.6 Blinding

This study will be single-blind (patient), as investigator blinding is not possible due to the visual and physical difference between the 2 treatment regimens. Patients will be kept blinded throughout the study. In addition, the surgeon performing the surgery will remain blinded until intra-operative entry criteria have been confirmed (see Section 5.2).

Otherwise, investigators, surgery personnel, site study personnel, clinical research organisation personnel, and sponsor personnel will not be blinded. Adequate block size will be used to prevent guessing the allocation in the trial and to ensure real blinding. Flexible random block sizes will be also used based on the stratification factors (site and surgical region), eg, relative small block sizes will be used to maintain balance in small strata whereas relative large block sizes will be used in large strata.

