6.8.3 Toxicity Grading Scale

Laboratory values will be evaluated according to the CTCAE Version 4.03 toxicity grading scale and captured on the eCRF by the investigator. Grades 3 and 4 will be considered AEs and reported appropriately. The laboratory parameters and the corresponding grading scale are provided in [Appendix 5](#). Laboratory parameters not covered by the CTCAE toxicity scale will be evaluated according to normal values assigned by the local laboratory.

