6.13.7 Clinical Laboratory Adverse Events

The investigator's assessment of each relevant laboratory value will be recorded on the eCRF. For each abnormal laboratory value, the investigator will determine whether the value is considered clinically significant or not. For clinically significant values, the investigator will indicate if the values constitute a new AE and record the sign, symptom, or medical diagnosis on the AE eCRF. The investigator will also record on the AE eCRF

whether the clinically significant values are symptoms or related to previously recorded AEs, are due to pre-existing diseases, or are due to other issues. Adverse events that are grade 3 and 4 will be considered AEs and reported appropriately. The laboratory parameters and the corresponding grading scale are provided in [Appendix 4](#). Additional tests and other evaluations required to establish the significance or aetiology of an abnormal value or to monitor the course of an AE should be obtained when clinically indicated. Any abnormal value that persists should be followed at the discretion of the investigator.

Any seroconversion result for HIV, HAV, HBV, HCV, hepatitis E virus (HEV), or parvovirus B19 (B19V) shall be re-tested.

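### Laboratory shift tables split abnormal values only by the unblinded investigator's clinical-significance call; adding shifts by the CTCAE grade already collected is a cheap improvement

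*SAP*

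**What the plan says.** SAP section 11 plans the laboratory shift tables thus: "Shift tables for baseline vs. worst post baseline assessment (normal, abnormal/not clinically significant, abnormal/clinically significant) will be generated for laboratory parameters". SAP 13.1 lists them as Tables 14.3.4.1.1 (haematology), 14.3.4.2.1 (chemistry) and 14.3.4.3.1 (coagulation). Below, NCS and CS stand for abnormal without and with clinical significance.

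Protocol 6.13.7 says who decides: "For each abnormal laboratory value, the investigator will determine whether the value is considered clinically significant or not". Neither document gives a numerical rule for that decision. On blinding, protocol 5.6 says that "investigators, surgery personnel, site study personnel, clinical research organisation personnel, and sponsor personnel will not be blinded", apart from the surgeon before intra-operative entry is confirmed.

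Protocol 6.8.3 also requires a rule-based classification: "Laboratory values will be evaluated according to the CTCAE Version 4.03 toxicity grading scale and captured on the eCRF by the investigator". The limits are in Appendix 5. For the rest, "Laboratory parameters not covered by the CTCAE toxicity scale will be evaluated according to normal values assigned by the local laboratory". The SAP text never mentions CTCAE, and no table in SAP 13.1 is laid out by grade.

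The shift tables are not the only laboratory output. SAP 11 plans summaries by visit and treatment group: "Absolute values and changes from baseline will be presented". SAP 13.1 adds listings of abnormal haematology, chemistry and coagulation values. Protocol 6.8.3 states: "Grades 3 and 4 will be considered AEs and reported appropriately".

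**The concern.** A shift table shows how far each patient's worst value moved from baseline, by arm. Here the step from NCS to CS is an opinion given by someone who knows the treatment. Two identical values could be placed differently at different sites or in different arms. The two abnormal levels also carry no grade and no direction.

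Laboratory values are a named secondary safety endpoint (protocol 9.4.4), and safety is the trial's secondary objective. A rule-based alternative is already being recorded and goes unused. At stake is how far one descriptive safety display can be trusted and how much it tells the reader.

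**Working it through.** The plan gives no figure on this point to reproduce, so the check is a cross-reading and a count.

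**1. Timing of the judgement.** SAP 5.2 sets baseline at the screening visit, which protocol 7.2 places on Days -30 to -1. Protocol 5.2 and 7.3 place randomisation on Day 0, and 5.2 has the arm revealed to the surgeon during surgery. Assuming each call is made when the result is reviewed, the baseline call is made without knowledge of the arm and the post-baseline call with it. A shift between NCS and CS can then mix real change with a change in what the rater knows.

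**2. Grade.** In Appendix 5, ALT is Grade 1 from just above ULN to 3.0 × ULN and Grade 4 above 20.0 × ULN. Both can be CS. A patient who goes from Grade 1 judged CS to Grade 4 judged CS shows no shift.

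**3. Direction.** Appendix 5 grades haemoglobin, WBC, calcium, sodium and potassium separately for high and low. The planned categories merge the two, so a move from low to high can also appear as no shift.

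**4. Coverage of the CTCAE scale.** Protocol Table 1 (chemistry, haematology, coagulation) against Appendix 5:

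| Group | In Table 1 | Graded | Not graded |
|---|---|---|---|
| Chemistry | 16 | 9: ALT, albumin, ALP, AST, bilirubin, calcium, creatinine, potassium, sodium | 7: bicarbonate, BUN, CRP, chloride, glucose, HbA1c, total protein |
| Haematology | 5 | 3: haemoglobin, WBC, platelets | 2: haematocrit, RBC |
| Coagulation | 3 | 2: INR, aPTT | 1: prothrombin time |
| Total | 24 | 14 | 10 |

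14 / 24 = 58%. Of the 10 ungraded analytes, HbA1c is scheduled only at screening and prothrombin time has no row in Appendix 4, so as scheduled neither could show a shift.

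**5. Gaps in Appendix 5.** For WBC increase the only entry is above 100000/mm³, under Grade 3. With grade alone, every raised WBC up to that value would score 0. Platelets are graded only for decrease. Low sodium has the same range under Grades 3 and 4, and low potassium the same range under Grades 1 and 2.

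**6. What depends on the significance call.** Only the NCS/CS split does. If normal means inside the local reference range, the normal/abnormal boundary does not. Nor do the numerical summaries, the changes from baseline or the listings of results.

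**The case against.** The strongest reply is that the planned laboratory package is adequate without the grades. Values and changes from baseline are summarised by arm with no opinion involved, abnormal values are listed, Grade 3 and 4 values should reach the AE tables, and no between-arm test of laboratory values is planned.

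Most of this stands, and it rules out two readings that a reader might infer. The first is that the whole laboratory comparison is biased. The documents do not support this, because only the NCS/CS split inside the shift tables rests on judgement. Nor do they present the shift table as the principal or objective laboratory comparison. The second is that severity is hidden. It is obscured in the shift tables but still visible in the listings and, for Grades 3 and 4, meant to appear as AEs.

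The other outputs are still not a substitute. Visit summaries describe group distributions at planned time points, not each patient's worst grade against baseline, and SAP 7.6 only lists unscheduled data. Listings give no counts by arm. AE severity uses the investigator's mild/moderate/severe scale (protocol 6.13.3), so the AE tables do not restore the CTCAE grade and cannot show Grade 1–2 shifts.

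A third tempting reading is that grades should simply replace the present categories. Step 5 speaks against it: elevated WBC is the first laboratory example in the safety endpoint, and a grade-only table would drop nearly all of it.

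It is also fair that the eCRF grade is entered by the same unblinded investigator. Its advantage is that it follows numerical limits and can be checked or derived by program. Protocol 6.8.2 has haematology and chemistry run at each site, and the documents do not say that local limits are captured, so program derivation may not be possible everywhere.

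**Conclusion.** The point holds as a cheap improvement of minor weight. The three shift tables separate abnormal values only by an unblinded judgement with no stated rule, they lose grade and direction, and they leave unused a grade that the protocol already collects. The size of any resulting bias cannot be computed from the documents; the exposure is to differential NCS/CS classification by arm. Rule-based grading can cover 14 of 24 analytes, so it supplements the present categories and cannot replace them.

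This rests on two assumptions: that significance is judged when each result is reviewed, and that normal means within the local range. The display is descriptive, and the primary non-inferiority conclusion does not depend on it.

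**What to change.** In SAP 11 and alongside Tables 14.3.4.1.1, 14.3.4.2.1 and 14.3.4.3.1:

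- Add shift tables of baseline against worst post-baseline CTCAE grade for the 14 graded analytes, with high and low directions shown separately.
- Derive the grade by program from the numeric value and local limits where these are available; otherwise use the eCRF grade, and say which was used.
- Use low/normal/high by local range for the 10 ungraded analytes (where a post-baseline value exists) and for directions that Appendix 5 does not grade fully, notably WBC increase and platelet increase.
- Keep the NCS/CS call as a supplementary display.
- Before programming, reconcile the shared ranges in Appendix 5 (low sodium Grades 3 and 4; low potassium Grades 1 and 2). Also correct the reference in protocol 6.13.7, which points to Appendix 4 for a grading scale that is in Appendix 5.

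No new assessments are needed. The cost is SAP wording, the Appendix 5 and cross-reference corrections, extra programming, and handling of units and local ranges across sites. The remaining limitation is grade coverage of 14 of 24 analytes.
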